## **Study Design**

This research will be conducted in two main phases:

Phase I: Cross-sectional study to assess baseline levels of depression and anxiety using validated tools.

Phase II: Randomized controlled trial (RCT) with two groups:

- Intervention Group: Receives structured, home-based walking exercise program for 6 months.
- Control Group: Receives standard care without exercise intervention.

Post-intervention assessment will be conducted for both groups after 6 months using the same tools.

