## **Sample Size and Sampling Technique**

Using Cochran's formula for finite populations, with a total population of 132, a 95% confidence interval, 5% margin of error, and an estimated prevalence of depression of 73%, the calculated sample size is 54 participants.

Sampling Method: Simple random sampling from the list of eligible patients at Al Suwaiq Renal Dialysis Center.

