### **Data Analysis Plan**

Data entry and cleaning using SPSS v22; Descriptive statistics for demographics and baseline variables; Baseline comparisons using t-tests or non-parametric equivalents; Paired t-tests for within-group changes; Independent t-tests for between-group differences; Significance set at  $p < 0.05$  (two-tailed).

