### **Ethical Considerations**

Ethical approval will be obtained from the Institutional Research and Ethics Committee. Informed consent will be taken from all participants. Confidentiality will be maintained, and participants can withdraw anytime without affecting their treatment.

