The Effect of Non-Pharmacological (Home-Based Exercise) Intervention on Psychological Distress of Patients Undergoing Hemodialysis at Al Suwaiq Renal Dialysis Center

NCT07083843

Date:15/08/24

Study Objectives

Primary Objective: To evaluate the effect of home-based exercise on reducing psychological distress (depression and anxiety) in patients undergoing hemodialysis.

Secondary Objective: To describe the baseline prevalence and severity of depression and anxiety among hemodialysis patients.

Study Design

Phase I: Cross-sectional assessment of depression and anxiety levels using the University of Michigan Depression Center's tools.

Phase II: Randomized controlled trial (RCT) with intervention and control groups.

Phase III: Post-intervention reassessment after 6 months.

Study Population

Sample size: Initially 132 screened → 54 enrolled → 26 participants per group in final analysis.

Inclusion/Exclusion Criteria: As defined in the study protocol.

Variables

Primary Outcomes: Depression Score (0-27) using PHQ-9 scoring; Anxiety Score (0-21) using GAD-7 scoring.

Independent Variable: Intervention group assignment (Home-based exercise vs. Control).

Covariates: Age, gender, duration of dialysis, comorbidities.

Data Collection Method

Face-to-face interviews for questionnaire administration. Baseline data from Al Shifa system (demographics, clinical history).

Statistical Analysis

- Data Management: Data entry and cleaning in SPSS v22. Descriptive statistics for demographics and baseline variables: Continuous variables: Mean ± SD (or median and IQR if non-normal). Categorical variables: Frequencies and percentages.
- Baseline Comparisons: Independent t-test, Chi-square, or Fisher's exact test for categorical variables.

Main Analysis: Paired t-test for within-group changes; Independent t-test for between-group differences in change scores.

- Significance Level: p-value < 0.05 considered significant; two-tailed tests.

- Handling Missing Data: Intention-to-treat principle; Last Observation Carried Forward method for missing values.

Presentation of Results

Tables for baseline demographics, pre- and post-intervention scores. Paired t-test results with mean difference, 95% CI, and p-value. Graphical representation of score changes.

Ethical Considerations

Analysis will be performed on anonymized datasets. Results will be reported in aggregate without identifying participants.

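### With a single follow-up, LOCF sets the change of anyone without a 6-month score to exactly zero, and 2 of the 54 enrolled are unaccounted for

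*SAP*

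**What the plan says.** The SAP's rule for missing data is "Intention-to-treat principle; Last Observation Carried Forward method for missing values". Its main between-arm test is "Independent t-test for between-group differences in change scores", alongside paired tests within each arm.

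Both documents describe one baseline assessment and one later assessment. The Protocol (Study Design) says "Post-intervention assessment will be conducted for both groups after 6 months using the same tools". The SAP (Study Design) has "Phase III: Post-intervention reassessment after 6 months". Neither mentions an interim visit.

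On numbers, the Protocol (Sample Size and Sampling Technique) says "the calculated sample size is 54 participants", from a formula for estimating a prevalence. The SAP (Study Population) lists 54 enrolled and then "26 participants per group in final analysis". Neither document gives the number randomised.

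The Protocol's Data Analysis Plan lists "Paired t-tests for within-group changes; Independent t-tests for between-group differences" but names no analysis set and no missing-data rule.

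**The concern.** LOCF is usually described for trials with several visits, where the last value may come from part-way through treatment. Here the only value that can be carried forward is the baseline, so the rule amounts to assuming that everyone without a 6-month score did not change at all. That assumption goes straight into the variable being tested. It also pulls the within-arm paired results toward zero, and those are the only results for which the SAP promises a confidence interval.

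Missing scores could well differ between arms. One arm is asked to follow a home programme for 6 months, and the Protocol (Ethical Considerations) notes that "participants can withdraw anytime without affecting their treatment". If they do differ, and scores drift over the period, the arm difference is shifted by something other than treatment.

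The participant flow raises a second question. If the two people missing from the final analysis were randomised, intention-to-treat with LOCF would have kept them, and the set should be 54. If they left before randomisation, 52 may be the complete randomised set. The reader cannot tell which.

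**Working it through.** **Inputs from the documents.** One baseline and one 6-month score; change scores compared by t-test; two-sided 5% level; 54 enrolled; 26 per arm analysed.

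**Assumed, because the documents give no values.** 27 per arm (54/2), true effect 0.8 SD, baseline-to-6-month correlation 0.6, normal scores with SD 1, dropout unrelated to the scores, and a range of dropout and drift. Dropout here means having no 6-month score. A participant who stops exercising but is reassessed is not imputed.

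**Step 1: flow.** 2 × 26 = 52; 54 − 52 = 2; 2/54 = 3.7%.

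**Step 2: what the rule does.** The imputed 6-month score equals the baseline score, so the imputed change is baseline − baseline = 0.

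**Step 3: expected estimate.** Let mI and mC be the dropout fractions in the intervention and control arms, and let drift be the change common to both arms (positive = worsening). Mean LOCF change is (1 − mI)(drift − effect) in the intervention arm and (1 − mC) × drift in control. Subtracting gives

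expected LOCF benefit = (1 − mI) × effect + (mI − mC) × drift.

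**Step 4: equal dropout, no drift.** The estimates follow the formula, for example 0.8 × 0.8 = 0.64 and 0.7 × 0.8 = 0.56. Coverage comes from 20,000 simulated trials per case; repeat runs agree to about one percentage point.

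| Missing in each arm | LOCF estimate (true 0.80 SD) | Coverage of 95% interval |
|---|---|---|
| 1/27 (3.7%) | 0.77 | 95% |
| 10% | 0.72 | 94% |
| 20% | 0.64 | 89% |
| 30% | 0.56 | 79% |

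The average standard error matches the empirical one (0.225 against 0.226 at 20%; 0.214 against 0.215 at 30%). The lost coverage is therefore due to bias, not to an understated standard error.

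**Step 5: unequal dropout with drift, effect 0.8 SD.**
- 30% intervention, 10% control, both arms drifting 0.5 SD worse: 0.7 × 0.8 + 0.2 × 0.5 = 0.66.
- Same dropout, both arms drifting 0.5 SD better: 0.56 − 0.10 = 0.46.
- 10% intervention, 30% control, drifting 0.5 SD better: 0.9 × 0.8 + (−0.2)(−0.5) = 0.82, slightly away from zero.

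**Step 6: no true effect, 30% intervention against 10% control.** The false benefit is 0.2 × drift.

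| Drift (worsening) | False benefit | Type I error |
|---|---|---|
| 0 | 0 | 5.0% |
| 0.3 SD | 0.06 SD | 6.1% |
| 0.5 SD | 0.10 SD | 7.5% |

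On a points scale, assume SD of change 5, both arms changing by 3 points, and 30% against 5% dropout. The false difference is 0.25 × 3 = 0.75 points, with type I error about 9%.

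**Step 7: the loss the documents show.** One missing per arm: (26/27) × 0.8 = 0.77 SD, coverage 95%. Both in one arm with 0.5 SD drift and no true effect: (2/27) × 0.5 = 0.04 SD, type I error 5.3%.

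**The case against.** The strongest reply is that nothing material happens at the loss actually shown. With 2 of 54 missing, bias and error rates are close to nominal. Every serious figure needs 20–30% missing, and the type I error results also need drift; the documents give neither. With equal dropout and no drift the bias is toward zero, which works against the trial's own hypothesis. With no effect and no drift, even 30% against 10% dropout leaves type I error at 5%. The case of bias away from zero is small: 0.82 against 0.80 SD, with coverage still about 95%. A right to withdraw does not show that 6-month scores will be missing, since participants come from one dialysis centre's list and are interviewed face to face.

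All of that is fair and limits the size of the point. It does not rescue the rule. An analysis plan has to work for whatever dropout occurs, and this rule is not reliably conservative: unequal dropout with drift produces a false effect when there is none.

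It is also fair that the 54-to-52 gap is a request for clarification rather than a demonstrated error. Enrolled is not the same as randomised, and Phase I comes before the trial phase.

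Finally, setting LOCF change scores against a baseline-adjusted analysis changes two things at once. Dropping LOCF but keeping the change-score t-test would cost more: the standard error would go from 0.225 to about 0.272 at 20% missing (+21%), and from 0.214 to about 0.294 at 30% (+37%). The baseline adjustment recovers part of that.

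**Conclusion.** The concern holds and should be fixed. That LOCF gives a change of exactly zero follows from the documents alone. How far this distorts the result depends on dropout, effect and drift, which the documents do not give. It is negligible at 3.7% missing, a 20% shrinkage of the effect at 20% missing in both arms, and 30% at 30%, with coverage of about 89% and 79% under the assumptions above. Unequal dropout combined with drift can shift the estimate either way and raise type I error to roughly 6–9% in the cases examined.

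Whether the two unaccounted-for participants were randomised cannot be settled from the documents. If they were, a 52-person analysis contradicts the SAP's own intention-to-treat rule; if not, there is no conflict. On its own that gap calls only for clarification.

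**What to change.** In the SAP:

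- Define the primary analysis set as all randomised participants, analysed in their assigned arm.
- Replace "26 participants per group in final analysis" with the number randomised per arm, and state at which step the other two left.
- State that missing means no 6-month score, and that anyone reassessed is analysed on the observed score.
- Replace LOCF with a likelihood-based repeated-measures model for the baseline and 6-month scores, or baseline-adjusted ANCOVA with multiple imputation. With about 27 per arm, use one small imputation model that includes arm and baseline score.
- Add a missing-not-at-random sensitivity analysis that shifts the imputed 6-month scores separately in each arm over a stated range.
- Keep zero-change LOCF only as a sensitivity analysis.

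The Protocol's Data Analysis Plan should then be brought into line.

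The cost is SAP wording and slightly more analysis work, with no new data. Intervals widen. In the simulation, baseline-adjusted analysis of the observed 6-month scores has standard error 0.246 against 0.225 for LOCF at 20% missing (+9%), and 0.264 against 0.214 at 30% (+23%). In return the estimate is 0.80 SD with 95% coverage at both rates. This was simulated with dropout unrelated to the scores; the imputation and missing-not-at-random analyses were not themselves simulated.
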